### **5.2.2 Packaging and Labeling Information**

Clinical supplies will be affixed with a clinical label in accordance with regulatory requirements.

### **5.2.3 Clinical Supplies Disclosure**

The subject, the trial site personnel, the Sponsor and/or designee are not blinded to treatment. Drug identity (name, strength) is included in the label text; random code/disclosure envelopes or lists are not provided.

### **5.2.4 Receiving, Compliance, Storage and Return Receipt of Drug Supplies**

Metformin and doxycycline tablets will be provided by the Department of Medical Oncology and will be coordinated through the Thomas Jefferson University Hospital Investigational Drug Service (IDS) Pharmacy. Drug will be stored in locked cabinet until given to the participants. A study investigator will prescribe the approximate amount of medication needed for the treatment period, and the metformin and doxycycline will be self-administered by the participants based on dose escalation timeline and study treatment follow-up phone calls.

Upon receipt of the of the study treatment supplies, an inventory must be performed and a drug receipt log filled out and signed by the person accepting the shipment. It is important that the designated study staff counts and verifies that the shipment contains all the items noted in the shipment inventory. Any damaged or unusable study drug in a given shipment (active drug or comparator) will be documented in the study files. The investigator must notify study sponsor of any damaged or unusable study treatments that were supplied to the investigator's site. At the completion of the study, there will be a final reconciliation of drug shipped, drug consumed, and drug remaining. This reconciliation will be logged on the drug reconciliation form, signed and dated. Any discrepancies noted will be investigated, resolved, and documented prior to return or destruction of unused study drug. Drug destroyed on site will be documented in the study files.

### **Subject Compliance Monitoring**

There will be two pill bottles with the appropriate number of metformin and doxycycline tablets distributed to the patients upon enrollment into the trial. The pill bottles will be accompanied with a pill diary for each medication and detailed instructions on the proper dosage/number of tablets to take daily as noted above. Upon arrival for definitive surgical resection, the diaries and bottles will be collected by our trial coordinator and the contents will be evaluated for compliance.

### **Storage Requirements**

Drug will be stored in a locked cabinet until given to the participants at room temperature in the coordinated through the Thomas Jefferson University Hospital Investigational Drug Service (IDS) Pharmacy. Access to the locked cabinet will only be granted to the study coordinator. The investigator must ensure that it is stored in accordance with the environmental conditions as defined in the Investigator Brochure. Clinical supplies may not be used for any purpose other than that stated in the protocol.

### **Returns**

The investigator is responsible for keeping accurate records of the clinical supplies received from the Sponsor or designee, the amount dispensed to the subjects and the amount remaining at the conclusion of the trial.

Upon completion or termination of the study, all unused and/or partially used investigational product will be destroyed at the site per institutional policy. It is the Investigator's responsibility to arrange for disposal of all empty containers, provided that procedures for proper disposal have been established according to applicable federal, state, local and institutional guidelines and procedures, and provided that appropriate records of disposal are kept.

### **5.2.5 Dose Limiting Toxicity Criteria**

Dose-limiting toxicities (DLTs) will be graded in severity according to the guidelines outlined in the NCI- CTCAE version 4.03. Dose-limiting hematologic and non-hematologic toxicities will be defined differently, and will be based on events that occur during study drug administration and for 30 days after the completion of the therapy. In order to be declared a dose-limiting toxicity, an adverse experience must be related (definitely, probably, or possibly) to study therapy.

## **5.3 Surgical Resection**

Surgical Resection will occur immediately following the last scheduled dose of metformin and doxycycline. Surgical technique to be used will be at the surgeon's discretion. Every effort should be made to have tumor tissue flash frozen as quickly as possible after resection. AEs

and concomitant medications will be evaluated and recorded prior to surgery. Adverse events and concomitant medications considered by the Investigator to be related to surgical resection will be recorded in appropriate source documentation; however, such AEs and concomitant medications will not be recorded on CRFs.

## 5.4 Concomitant Medications/Treatments

Medications or vaccinations specifically prohibited in the exclusion criteria are not allowed during the ongoing trial. If the patient is on any of the Class C medications as outlined in Section 5.4.2, they should be monitored closely for any potential interactions or side effects. If there is a clinical indication for one of these or other medications or vaccinations specifically prohibited during the trial, discontinuation from trial therapy or vaccination may be required. The investigator should discuss any questions regarding this with the Sponsor. The final decision on any supportive therapy or vaccination rests with the investigator and/or the subject's primary physician. However, the decision to continue the subject on trial therapy or vaccination schedule requires the mutual agreement of the Investigator, the Sponsor, and the subject.

### 5.4.1 Acceptable Concomitant Medications

All treatments that the investigator considers necessary for a subject's welfare may be administered at the discretion of the investigator in keeping with the community standards of medical care. All concomitant medication and therapies will be recorded on the case report form (CRF) including all prescription, over-the-counter (OTC), herbal supplements, and IV medications and fluids. If changes occur during the trial period, documentation of drug dosage, frequency, route, and date should also be included on the CRF. These will be cross referenced against the list of drugs in section 4.2 (Exclusion Criteria) to ensure that no agents that are contraindicated with metformin or doxycycline are used.

All concomitant medications received within 28 days before informed consent is signed and 30 days after the last dose of trial treatment should be recorded. Concomitant medications administered to treat SAEs and ECIs should be recorded as defined in Section 8.2

### 5.4.2 Prior and Concomitant Medication

All medications are permitted except those that are contraindicated with metformin and doxycycline under current FDA recommendations. It is important to note that the medications that are contraindicated with metformin are contraindicated due to concern for theoretical interactions. Class C medications are allowed if they are established at baseline. The treating physician should be made aware of any new Class C medications taken during therapy for proper monitoring of potential interactions. The following is a list of medications identified as class C (monitor therapy) and class D (consider therapy modification) when treatment with metformin or doxycycline is considered:

#### Class C:

Carbonic anhydrase inhibitors  
Cephalexin  
Corticosteroids (orally inhaled)  
Corticosteroids (systemic)  
Dalfampridine  
Dofetilide  
Glycopyrrolate  
Lamotrigine  
Luteinizing hormone-releasing hormone analogs

#### Class D:

Bismuth Subsalicylate  
Cimetidine  
Iodinated contrast agents  
Somatropin

Pegvisomant  
Penicillin  
Trosipium

### **5.5 Dietary Restrictions**

Subjects should maintain a normal diet unless modifications are required to manage an AE such as diarrhea, nausea or vomiting. Patients will be asked to fill a dietary log at the beginning the study when they speak with a registered dietician.

C. Study treatment follow-up phone calls will occur on days 3 ±2 days and 5 (± 2 days) of dose escalation to evaluate tolerability, document AEs, and concomitant medications. If patient remains on study drugs for >7 days, study treatment follow-up phone calls will occur a minimum of once a week until surgery to evaluate tolerability, AEs, and con meds. Last doses of Metformin and Doxycycline pills should not be taken up to 12 hours before scheduled surgery time.

D. Patient must receive a minimum of 7 days of metformin and doxycycline before having definitive cancer surgery. Patients will stay on metformin and doxycycline until the day prior to surgery (up to the maximum of 5 weeks).

E. End of treatment visit may occur within 21 days ±7 days of stopping study drug.

F. Correlative study blood to be collected the morning of surgical resection.

- G. Follow up phone call will be performed 30 days ( $\pm$  5 days) after last dose of study medication for any other side effects or toxicity. Subject medical records will be reviewed every 3 months ( $\pm$  1 month) for 12 months.
- H. Urine or blood pregnancy test must be done within 14 days prior to enrollment on study for all women of childbearing potential.
- I. Physical examinations should include vital signs, weight and blood pressure
- J. Screening physical examination should include height.
- K. Concomitant medication reconciliation, and Toxicity and Adverse Event assessments should be done at every patient contact to fully capture any potential dose limiting toxicities or AEs that affect the patient's ability, willingness, and eligibility to continue taking study medications.
- L. Operative reports should be included with pathology reports in source documents when applicable.
- M. This optional assessment should be performed by a registered dietician. When applicable, the RD will meet with the patient within seven days of enrollment and record the patient's last 3 days of caloric intake and estimate their caloric intake versus their caloric needs per the Harris Benedict Equation.
- N. Tumor tissue should be flash frozen as quickly as possible after resection.
- O. Baseline tissue specimen will be obtained for comparative analysis when available.

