**\* If surgery is scheduled past Day 8, patients will stay on metformin and doxycycline until the day prior to surgery.**

- a. Metformin will be given initially with a starting dose of 500mg once a day for Days 1-3.
- b. Metformin will be increased to 500 mg orally twice a day for Days 4-6
- c. If tolerated, beginning Day 7 metformin will be increased to 1000 mg twice a day. Subjects will maintain the maximum tolerated dose (up to 1000 mg twice daily) until the day prior to their scheduled definitive surgery.
- d. When possible, baseline biopsy tissue is to be obtained prior to starting study medications. Two serum separator tubes of serum will be taken at the same time as the biopsy specimen (if possible), otherwise done at time of consent. If a pre-treatment sample has already been acquired and flash froze and if there is excess tissue available at resection, the second specimen will also have a piece flash frozen for metabolomic testing.
- e. Doxycycline will be taken once every 12 hours, with the last dose being taken at least 12 hours prior to scheduled time of definitive surgery.

Metformin and doxycycline are the therapeutic agents. For metformin, the initial starting dose will be 500 mg orally daily for 3 days which will then be increased to 500 mg orally twice daily, and if tolerated, further increased to 1000 mg twice daily after day 6. Subjects will maintain the maximum tolerated dose (up to 1000 mg twice daily) until the day prior to their scheduled definitive surgery.

For doxycycline the patients will take 100 mg by mouth every twelve hours until the day prior to their surgery.

**Criteria for  
Evaluation:**

Primary:

- Assess the impact of metformin and doxycycline on the percentage of cancer associated fibroblasts that stain with 1+ intensity or greater for CAV1 by immunohistochemistry (IHC) pre and post metformin and doxycycline exposure as determined by two blinded pathologists. All patients from whom samples are obtained both pre- and post-treatment will be included in the primary analyses.

Secondary:

- Assess the impact of metformin and doxycycline on the percentage of cancer-associated fibroblasts that express MCT4 and the percentage of cancer cells that express MCT1 and TOMM20. All patients from whom samples are obtained both pre- and post-treatment will be included in the secondary analyses.

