*Correlative:* Mass spectroscopy imaging (MSI) will be performed on paired samples from the three subjects, comparing metabolite profiles including ATP, hexose bisphosphates, lactate and pyruvate in the pre-treatment and post-treatment tumor sample. MSI will allow spatial characterization of the metabolic profile of carcinoma and stromal cells within the tumor. MSI will also allow us to determine if distance between carcinoma and stromal cells is associated with different metabolite profiles. MSI testing will be performed at Vanderbilt University as has been performed in the ongoing metformin HNSCC. This testing is performed outside of the KCC because we lack the facilities and expertise for MSI. We will also send tumor samples from our tumor bank, from patients who have not taken metformin or doxycycline, to use as controls. We will also further characterize the baseline metabolic state of the patient by performing, when possible, a nutritional assessment via a nutritionist-mediated 3 day dietary recall and comparing a patient's estimated dietary intake against their estimated caloric needs calculated with the Harris-Benedict equation. This will determine if patients are already calorically restricted, a phenotype similar to that of mitochondrial blockade. Similarly we will do a serologic assessment of their metabolic state will also be performed at the time of enrollment and at the time of resection using the serum markers oncomiR-21, triglycerides, IGF-1, IGF-BP3, ESR, IGFR-1, exosomes, metabolomics, and microRNA expression profiles. These serologic assays have been shown to correlate both with nutritional state and in the case of miR21 with tumor burden.

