### 2.1.3 Correlative

- To assess the effect of combined metformin and doxycycline therapy on the metabolic profile of cancer cells and stroma using mass spectroscopy imaging (MSI) on paired samples, comparing metabolite profiles in the pre-metformin and post-metformin tumor sample.
- To assess, when possible, the impact of a patient's nutritional status, estimated using 3-day dietary recall versus caloric needs as calculated by the Harris-Benedict equation on the baseline and net change in CAV1.
- To assess the effect of combined metformin and doxycycline therapy on oncomiR miR-21 after intervention.
- To assess the effect of combined metformin and doxycycline therapy on adipokines and the IGF-1/insulin signaling pathways through assessment of serum triglycerides, IGF-1, IGF-BP3, erythrocyte sedimentation rate (ESR), adiponectin, leptin, IGF-1R, exosome evaluation, metabolomics profile, and microRNA expression profile.

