**Visit 1, Day 0:** Subjects that meet the inclusion criteria after reviewing diagnosis, laboratory data and clinical chart will be approached the day of their consult or follow up with a subspecialty surgeon. The study coordinator will meet with the prospective candidates and go over the protocol, answer questions and obtain informed consent. If the subject is agreeable to the study, two 8.5 mL vials of blood will be drawn for baseline metabolomics and exosome profiling. After eligibility is confirmed, metformin and doxycycline will be dispensed. Instructions on how to take study drug will be given and times for follow up phone calls for tolerability and safety will be arranged with participants. When possible, patients will be given the option to meet with a nutritionist either in person or by phone within the first 7 days of their enrollment to fill out a 3 day dietary recall.

*Visit 2, Day of Surgery:* Patients will be approached for bottles and pill reconciliation as well as follow up of side effects and adverse events the day of final surgery. Two 8.5 mL vials of blood will be drawn for post-treatment metabolomic and exosome profiling. A specimen of the removed tumor will be taken for genomic analysis.

*Follow-up:* A follow up phone call will be performed 30 days ( $\pm 5$  days) after the last dose of metformin and doxycycline for any other side effects or adverse events. The participant's medical records will be reviewed every 3 months ( $\pm 1$  month) for 12 months to assess: overall survival, frequency of metastasis, and staging.

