### 6.3 Surgical Resection

The following study activities will occur on the day of surgical resection:

- Two SST red-top tubes of blood for correlative studies: oncomiR miR-21, serum triglycerides, IGF-1, IGF-BP3, ESR, adiponectin, leptin, IGF-1R, exosome evaluation, metabolomics profile, and microRNA expression profile.
- Definitive cancer surgery
  - Pathology report needed
  - Tumor tissue
    - Exosome evaluation, metabolomics profile, and microRNA expression profile.
- Return all Metformin and Doxycycline medication bottles (including any unused tablets/pills)
- Collection of pill diaries

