### 7.3.1 Correlative Studies

Serum studies as described above will be drawn anytime during the screening period and/up to Week 1 Day 1 and at the time of surgical resection.

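### Fasting state and clock time are unspecified for the baseline correlative serum, while the post-treatment sample is fixed to the morning of surgery, so exploratory serum changes cannot be separated from sampling conditions; ESR is also listed on serum tubes

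*Combined protocol and SAP*

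**What the plan says.** **Objective.** Section 2.1.3 states a treatment effect: "To assess the effect of combined metformin and doxycycline therapy on adipokines and the IGF-1/insulin signaling pathways through assessment of serum triglycerides", followed by IGF-1, IGF-BP3, ESR, adiponectin, leptin, IGF-1R, exosomes, metabolomics and microRNA. The Study Summary calls the serum work exploratory.

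**Second draw.** Study calendar footnote F: "Correlative study blood to be collected the morning of surgical resection".

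**First draw.** Several places describe it:
- Section 7.3.1 says serum studies "will be drawn anytime during the screening period and/up to Week 1 Day 1 and at the time of surgical resection".
- Footnote d to the design table, in the Study Summary and Section 3: "Two serum separator tubes of serum will be taken at the same time as the biopsy specimen (if possible), otherwise done at time of consent".
- Section 3, Visit 1, on the day of the surgical consult or follow-up: "two 8.5 mL vials of blood will be drawn for baseline metabolomics and exosome profiling".

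**Fasting.** Section 4.4 and calendar footnote B describe the screening safety tests as non-fasting. Section 5.5 asks for a normal diet. Neither correlative draw has a fasting instruction.

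**Sensitivity of the assays.** Section 1.2, Rationale for endpoints: "These serologic assays have been shown to correlate both with nutritional state".

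**Tubes.** Section 6.3 lists, for the day of surgery, "Two SST red-top tubes of blood for correlative studies: oncomiR miR-21, serum triglycerides, IGF-1, IGF-BP3, ESR" and further analytes. Section 7 names serum separator tubes at enrollment and at resection.

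**The concern.** The correlative objective attributes a within-patient serum change to the two drugs. That reading requires the two samples to differ in treatment and in little else that moves the markers. Here one sample is tied to a particular morning and the other is not tied to any condition. If fasting state or time of day differs between draws in a consistent direction, the difference enters the estimated change as bias, and more patients will not average it out. With no untreated serum series, nothing in the data would show how much of the change it explains.

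At stake is the interpretation of an exploratory mechanistic analysis. A fall in triglycerides or a shift in the metabolome could be read as a drug effect and carried into later work. Time since last meal cannot be recovered reliably afterwards, so the point has to be settled before samples are collected.

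The ESR point is separate. ESR is measured on anticoagulated whole blood (general laboratory knowledge, not stated in the documents), and the only tubes the protocol names for the correlatives are serum tubes.

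**Working it through.** The plan gives no sample size, test or effect size for the serum markers, so there is no figure to reproduce. The check sets the sections side by side and then adds an illustration.

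**1. Are the two draws matched?**

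| Condition | Baseline | Post-treatment |
|---|---|---|
| Calendar time | Screening up to Week 1 Day 1; with biopsy, at consent or at consult (7.3.1, footnote d, Section 3) | Day of surgery (6.3) |
| Clock time | Not stated | Morning (footnote F) |
| Fasting state | Not stated | Not stated; probably fasted (assumption) |
| Time since last meal | Not recorded | Not recorded |

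The draws are not standardised to each other, and no data item would allow a later correction.

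**2. Could another planned element separate the effects?**
- Tumor-bank controls (Section 1.2) are tumor samples for mass spectroscopy imaging, not serum.
- The dietary recall is optional, takes place once within seven days of enrollment, and is not repeated at surgery.
- Sections 10.1 to 10.3 specify no serum analysis or adjustment.

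None of these separates the effects.

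**3. How much could a mismatch matter?** The documents give no shift size, so a range is assumed. Let b be the mean change due to sampling conditions alone, in SDs of the change score, with zero drug effect. If a fraction f of pairs is mismatched and each mismatched pair shifts by s SD, then b = f × s. For example, half the pairs at 0.5 SD gives 0.5 × 0.5 = 0.25. Section 10.1 analyses each cohort separately, so the natural sizes are 23 (recruited) and 19 (the evaluable number in Section 10.4, used here only as a smaller case). The test is an exact two-sided Wilcoxon signed-rank test at 0.05, with normal changes and 4,000 simulations. The plan does not name a test for serum, so this is also an assumption.

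| b (SD) | 19 pairs | 23 pairs |
|---|---|---|
| 0 | 5% | 5% |
| 0.25 | 18% | 19% |
| 0.5 | 53% | 61% |
| 0.75 | 86% | 92% |
| 1 | 98% | 99% |

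Each entry is the chance of a nominally significant change with no drug effect. From 0.25 SD upward it exceeds 5% and is slightly higher with 23 pairs than with 19, as expected for bias rather than noise. The table shows what a shift of a given size would do. It does not show that such a shift exists.

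**4. ESR.** Section 6.3 puts ESR on two SST tubes on the day of surgery, and Section 7 names only serum separator tubes at both times. Table 3 lists ESR as a correlative. The study calendar schedules hematology at screening only, so it provides no whole-blood tube on the day of surgery.

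**The case against.** A reader might infer that the baseline is a non-fasting sample taken at any hour, and hence that all 46 pairs run from fed to fasted. The documents do not support this. The non-fasting wording covers only the screening chemistry and hematology. Section 7.3.1 sets a calendar window, not a clock time. A draw taken with the biopsy could itself be fasted. Pre-operative fasting is not mentioned anywhere. Serum is analysed only where samples exist, and by cohort. The mix of fed and fasted baselines is therefore unknown, and a fasting effect would pass in full into the estimate only if every pair were mismatched.

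The protocol's remark about nutritional state is also limited support. It follows the dietary recall and the comparison with caloric need, so it concerns sustained intake rather than hours since a meal.

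On ESR, a reader might infer that no valid measurement could be obtained. Section 7.3 leaves blood by visit and sample type to a Procedures Manual that is not available here, and Visit 1 gives vial volumes without a tube type. The protocol's tube list needs correcting, but a total loss of data is not shown.

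Finally, the analyses are exploratory, with no test or decision rule attached. A compulsory fasted morning baseline could require an extra visit, since consent and the baseline draw share the consult day and Section 6.2 requires no return on Day 1.

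These points limit the size and certainty of the concern. They do not remove it: an unknown, unrecorded mix of baseline conditions still leaves the change without a clear cause.

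**Conclusion.** The concern holds in a limited form. The timing mismatch, the absence of any fasting rule or meal-time record, and the lack of an untreated serum comparator are all in the text. Given these, a before-after change in triglycerides, adipokines, IGF-axis markers or metabolomics cannot be attributed to the drugs rather than to sampling conditions.

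The direction, size and consistency of any bias are unknown and may differ by marker. A fed-to-fasted contrast rests on two assumptions: that patients are fasted on the morning of surgery, and that a material share are not fasted at baseline. The simulated percentages apply only to the assumed shifts.

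The CAV1 primary endpoint, the tissue-based secondary endpoints, safety and the sample size are unaffected. This is a worthwhile, low-cost improvement to exploratory work. The ESR tube listing is a separate, minor correction that needs no fasting assumption.

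**What to change.** **Sampling conditions (Section 7.3.1 and calendar footnote F).**
- Record clock time and hours since last meal at both correlative draws.
- Where it needs no extra visit, prefer a fasted morning baseline within the existing window and before the first dose. Keep this a preference, not a requirement.
- In Section 10.3, state that serum changes will be reported by, or adjusted for, whether the pair is matched on fasting status, and that changes in unmatched pairs will not be attributed to the drugs. Adjustment is possible only if some pairs are matched, which is the reason for the preference above.

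**ESR.** Name an anticoagulated whole-blood tube at both draws, or delete ESR from the Study Summary, Sections 1.2, 1.3, 2.1.3 and 6.3, and Table 3. Align the Procedures Manual.

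**Cost.** Two CRF items at each draw, some wording, and either one added tube per draw or the loss of one exploratory marker. Fewer pairs will support a drug-effect reading. If few baselines prove to be fasted, that number could be small, and the serum results would then be descriptive only.

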**Table 1. Study Design**

Eligibility Screening	Cohort	Treatment	Week	-1	1							2							3	4	5
			Day	-1	1	2	3	4	5	6	7	8*	9	10	11	12	13	14			
	1 N=23	Doxycycline e			X	X	X	X	X	X	X	X	X	X	X	X	X	X	Surgical Resection		
		Metformin			X a	X a	X a	X b	X b	X b	X c	X c	X c	X c	X c	X c	X c				
	2 N=23	Doxycycline e			X	X	X	X	X	X	X	X	X	X	X	X	X	X			
		Metformin			X a	X a	X a	X b	X b	X b	X c	X c	X c	X c	X c	X c	X c	X c			
	Tissue d		X															X			

\* If surgery is scheduled past Day 8, patients will stay on metformin and doxycycline until the day prior to surgery.

- Metformin will be given initially with a starting dose of 500mg once a day for Days 1-3.
- Metformin will be increased to 500 mg orally twice a day for Days 4-6
- If tolerated, beginning Day 7 metformin will be increased to 1000 mg twice a day. Subjects will maintain the maximum tolerated dose (up to 1000 mg twice daily) until the day prior to their scheduled definitive surgery.
- When possible, baseline biopsy tissue is to be obtained prior to starting study medications. Two serum separator tubes of serum will be taken at the same time as the biopsy specimen (if possible), otherwise done at time of consent. If a pre-treatment sample has already been acquired and flash froze and if there is excess tissue available at resection, the second specimen will also have a piece flash frozen for metabolomic testing.
- Doxycycline will be taken once every 12 hours, with the last dose being taken at least 12 hours prior to scheduled time of definitive surgery.

**Eligibility Screening:** Trial Coordinator will screen the office charts for possible inclusion in the trial. Labs for the screening part will be available from pre-admission testing that is standard of care for initial biopsy. Participants of child bearing potential will have a pregnancy test within 14 days prior to enrollment.

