### 4.1 Subject Inclusion Criteria

In order to be eligible for participation in this trial, the subject must:

1. Diagnosis of localized breast, uterine or cervical cancer that is either biopsy proven or suspected based on history, physical, and/or radiographic findings, and who are planned for definitive resection of the tumor without the use of neoadjuvant chemotherapy or radiation therapy at TJUH are eligible to participate.
2. Subjects must be  $\geq 18$  years of age at time of consent.
3. Subjects must be newly diagnosed or suspected to have breast, uterine (endometrial cancer with histologies including endometrioid, serous, clear cell, and carcinosarcoma) or cervical cancer.
4. Patient must be able to swallow pills.
5. Patients with serum creatinine levels less than 1.5 mg/dL.
6. Women of child bearing potential must have a negative urine or blood pregnancy test within 14 days of study enrollment.
7. Informed Consent: All subjects must be able to comprehend and sign a written informed consent document.
8. ECOG Performance status  $\leq 1$

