### 10.4 Sample size justification

The sample in each cohort is based on having 80% power to detect an average increase in CAV1 staining of 20% using a one-sided Wilcoxon signed-rank test with  $\alpha=0.05$ . Based on pilot data in other cancers, we assume the standard deviation of change scores to be 32%. A sample size of 19 per cohort is required under these assumptions. Allowing for approximately 15% of patients to have missing pre- and or post-treatment data, we will recruit 23 women per cohort. Cohort 1 will consist of breast cancer patients and cohort 2 will include both uterine and cervical (gynecologic) cancers.

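### The primary analysis needs paired tissue but baseline tissue is optional; power holds to about 20% missing pairs, and requiring existing diagnostic tissue before dosing would be a cheap safeguard

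*Combined protocol and SAP*

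**What the plan says.** Section 2.2.1 defines the primary endpoint as the change in the percentage of stromal cells expressing CAV1. Section 10.2 includes in the primary analysis the patients who have both a pre- and a post-treatment sample.

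The baseline sample is conditional in two places:

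- Note O to the study calendar (Section 6): "Baseline tissue specimen will be obtained for comparative analysis when available".
- The notes to Table 1 (Section 3), repeated as note d in the Study Summary: "When possible, baseline biopsy tissue is to be obtained prior to starting study medications".

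Eligibility does not close the gap. Inclusion criterion 1 (Section 4.1) accepts disease that is "either biopsy proven or suspected based on history, physical, and/or radiographic findings", criterion 3 also accepts suspected disease, and Section 6.1 allows radiologic confirmation where appropriate. None of the eight inclusion criteria asks for a pre-treatment specimen.

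Section 10.4 does foresee losses. "A sample size of 19 per cohort is required under these assumptions", followed by "Allowing for approximately 15% of patients to have missing pre- and or post-treatment data, we will recruit 23 women per cohort". Section 4.5.1 replaces patients who are discontinued for a reason given in Section 4.5. Section 4.4 sets a maximum of 23 patients per cohort.

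**The concern.** A patient without baseline tissue has no change score and cannot enter the primary analysis, however complete the rest of the record. The protocol lets such a patient start both drugs and take them for one to five weeks. Section 1.4.1 says that significant clinical benefit to participants is unlikely, so the main justification for exposure is the information gained.

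There is little to fall back on. Section 4.5 lists reasons for discontinuation. Absent baseline tissue, an inadequate sample and a final pathology showing no cancer are not among them, so a patient who completes treatment without a baseline sample is not clearly replaceable. With 23 as a maximum, the 15% allowance has to absorb missing baseline tissue, missing post-treatment tissue and unusable samples together. Section 10.4 gives no source for the 15%, and nothing in the eligibility rules keeps the loss near it.

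**Working it through.** **Inputs (Section 10.4).** The design has "80% power to detect an average increase in CAV1 staining of 20" percentage points "using a one-sided Wilcoxon signed-rank test with" α = 0.05, and "we assume the standard deviation of change scores to be 32" percentage points. The standardised effect is 20/32 = 0.625.

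**Step 1: reproduce 19.** The plain normal formula gives ((1.645 + 0.842)/0.625)² = 15.8, so 16. The one-sided paired t-test (noncentral t) needs 18. Dividing by the asymptotic efficiency of the signed-rank test under normality, 3/π, gives 18 × π/3 = 18.85, so 19. This matches the plan. Simulating the exact one-sided signed-rank test with normally distributed changes gives power of about 0.81 at 19 pairs, 0.80 at 18 and 0.77 at 17.

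**Step 2: reproduce 23.** 19/(1 − 0.15) = 22.4, so 23. This matches. The margin is 23 − 19 = 4 unpaired patients, or 4/23 = 17.4%.

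**Step 3: vary the total share of missing pairs, m.** The documents give no observed rate, so m is an assumption. The number of pairs K is taken as Binomial(23, 1 − m). Mean power is the sum over k of P(K = k) × power(k), with power(k) from the exact signed-rank simulation. The last column is 19/(1 − m), rounded up.

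| m | P(K ≥ 19) | Mean power | Enrolment to expect 19 pairs |
|---|---|---|---|
| 10% | 0.93 | 0.84 | 22 |
| 15% (plan) | 0.74 | 0.82 | 23 |
| 20% | 0.50 | 0.80 | 24 |
| 25% | 0.28 | 0.77 | 26 |
| 30% | 0.14 | 0.74 | 28 |
| 40% | 0.02 | 0.67 | 32 |

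P(K ≥ 19) is a harsh yardstick, because 18 pairs still give about 0.80 power. At m = 15%, P(K ≥ 18) is 0.88.

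**Step 4: where the allowance ends.** Mean power stays at about 80% or more until m reaches roughly 20%, and falls below it after that. No tissue criterion, clear replacement rule or spare enrolment then makes up the shortfall.

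**The case against.** The strongest reply is that the plan has already dealt with this. Section 10.4 names missing pre- and post-treatment data, allows about 15%, and inflates correctly. A reader might infer from the conditional wording that the 80% power is unprotected. The documents do not support that, since at the plan's own rate mean power is 0.82 and at 20% it is still about 0.80.

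A reader might also equate suspected disease with no baseline tissue. That does not follow either. Eligibility on suspicion does not prevent a biopsy before the first dose. The Table 1 notes ask for one when possible, and the calendar places a diagnostic biopsy or tumour sample at screening. Section 1.1 describes endometrial biopsy, and colposcopy with biopsy, as the usual diagnostic route in the gynaecologic cohort. Section 7 has tumour biopsies fixed and embedded without condition, and only the freezing depends on excess tissue. Losses from absent baseline tissue may therefore be few.

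Some other losses may be replaceable, because the Section 4.5 grounds include investigator decision and administrative reasons. Unpaired patients also still inform safety, the toxicity stopping rule and the serum correlatives.

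All of this stands, and it limits the point to an improvement. It does not remove the route by which an unbiopsied patient is enrolled, treated and left out of the primary analysis. Nor does it reach the patient who completes treatment and so was never discontinued. Enrolling until 19 evaluable pairs are reached would also protect power, at about 0.81 whatever m is. It would need the cap in Section 4.4 changed, and would still treat patients who cannot contribute a pair.

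**Conclusion.** The concern holds as a cheap improvement, not as an error in the sample size. The figures 19 and 23 are right, and power is protected up to roughly 20% total missing pairs. What is missing is a basis for the 15%, any control on baseline tissue that would keep losses near it, and a clear rule for replacing a patient who completes treatment without a baseline sample. The falls to 0.74 at 30% and 0.67 at 40% show how sensitive the design is. They are not forecasts, because the actual rate cannot be derived from the documents.

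The power figures assume normally distributed changes with the plan's mean and standard deviation, and losses that are independent between patients and unrelated to the size of the change. The argument about exposure depends on neither the power model nor the loss rate.

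**What to change.** Add one criterion to Section 4.1: a pre-treatment tumour tissue specimen (existing diagnostic biopsy block or slides) is confirmed available before the first dose. Amend note O of the study calendar and the baseline-tissue note under the design table (Section 3 and Study Summary) to match, so that only the flash-frozen sample remains optional.

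No new study biopsy is needed, and no pathology read of the stroma before dosing, which would add a step to a short presurgical window. The 15% allowance then covers mainly post-treatment losses and inadequate samples. Under the fixed cap of 23, provided the cohorts still fill, the expected number of evaluable pairs can only rise.

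The cost is an eligibility amendment. Suspected-only patients without any biopsy would no longer be eligible, so enrolment may be somewhat slower and the safety set loses those few patients.
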